3 OBJECTIVES

3.1 PRIMARY OBJECTIVES

- To evaluate the acceptability, safety and use of a daily regimen of oral PrEP (FTC/TDF), as a component of a comprehensive HIV prevention package [with HIV testing, STI management, risk reduction counseling, access to condoms, PEP, counseling and referral for male circumcision (for boys)], for adolescents between 15 and 19 years of age.

3.2 SECONDARY OBJECTIVES

- To evaluate adherence to a daily regimen of oral PrEP (FTC/TDF), as a component of a comprehensive HIV prevention package for adolescents between 15 and 19 years of age.
- To evaluate change in sexual activity, perceptions of sexual risk, risk compensation, and health behaviours, including condom use, in adolescents, between 15 and 19 years of age, who take a daily regimen of oral PrEP (FTC/TDF) over a 12 month period.
- To assess study participants' and their partners' perceptions on key issues associated with oral PrEP (FTC/TDF), including adherence barriers, adherence facilitators, and general product knoweldge, as part of a comprehensive HIV prevention package [with HIV testing, STI management, risk reduction counseling, access to condoms, PEP, counseling and referral for male circumcision(for boys)].
- Incidence of HIV infection, as measured by seroconversion of study participants during the approximate 12 months (52 weeks) of follow-up.

3.3 EXPLORATORY OBJECTIVES

- To explore the utility of Dried Blood Spot (DBS)/Plasma drug levels and the impact of biofeedback of results as an adherence enhancing strategy among HIV-negative adolescents between 15 and 19 years of age
- To explore the relationship between daily PrEP usage and sexual practices and behavior in adolescents.

4 STUDY DESIGN

4.1 IDENTIFICATION OF STUDY DESIGN

We propose an open-label phase II cohort study, to evaluate the acceptability, safety and use of, daily oral PrEP (FTC/TDF) in 150 HIV-negative adolescents at two sites (approximately 75 participants at each site), ages 15-19 years, as well as adherence to medication in participants who choose to have biofeedback of drug levels versus those who choose not to and any changes in their sexual and health behaviors over a 12-month (52 week) period. Enrolled participants will be stratified by gender (33% Male: 66% Female). Out of the 75 participants at each site, approximately 25 adolescent males and 50 adolescent females will be enrolled. This oversampling of women is to account for the fact that although oral PrEP is relevant to both genders, young women are more vulnerable to HIV acquisition in South Africa.

After a period of community engagement and general education about prevention packages including PrEP, participants will be invited to screen for this study. Those who are considered eligible will be asked to return for an enrollment visit. At enrollment, all participants who still wish to take part will be asked to take PrEP as part of a comprehensive prevention package for at least 3 months (12 weeks). During the first 3 months (12 weeks), participants will attend monthly (4 weekly) clinic visits for adherence counselling, trouble shooting, HIV testing and dried blood spot/plasma drug level sampling.

Researchers will use dried blood / plasma drug level sampling, combined with the reporting of results to individuals by the next visit, as an adherence enhancing strategy for those participants who elect to receive this information during adherence counselling at follow up visits. Those participants who agree to it, will receive blood drug level results during personal counseling in month 2 and 3 (weeks 8 and 12). Those who choose not to get this information will receive standard motivational adherence counseling during their study visits. Study staff will explore through standard questionnaires the reasons for not receiving drug level data.

Participants will be asked at the 3-month visit whether they would like to continue PrEP for a further 3 months. Those who opt out will continue to be followed in all aspects of the study except for distribution of Truvada pills. All participants will receive a brief questionnaire to explore reasons

for continuing or stopping PrEP. A short acceptability questionnaire will also be administered. This opportunity to “opt out” or “opt back in” will occur at 3 monthly visits until Week 36. Followup will continue until week 48. Those who opt out at a 3 monthly visit will be asked whether they wish to restart at the next 3 monthly visit. Participants will also be advised that they may “opt out” of PrEP in their prevention package at any scheduled visit or at any time in consultation with clinic staff. They will be expected to return all study product and will not be issued TDF/FTC. They may “opt back in” on a subsequent study visit if all eligibility criteria are met and after a negative HIV test is obtained. At each study follow up visit, participants will be asked to grade their adherence on a visual scale, they will also be asked whether they wish to receive drug levels and their response and reasons for this will be captured. They will then receive motivational adherence counseling with or without drug levels depending on their choice at the time. Monthly scheduled visits will occur until month 3, thereafter scheduled visits will be 3 monthly.

Whilst every effort will be made to encourage adherence to PrEP in the first 3 months, poor adherence during those months will NOT preclude participation after 3 months. Every effort will be made to ascertain level of use and reasons for less than optimal use.

Additionally, two focus groups will be conducted at each site during the study period. The first focus group will be conducted prior to study initiation (within 3-4 weeks) with as yet non-enrolled participants from the community setting (n= 6-8). This size is recommended when conducting focus groups on non-commercial topics (Krueger, R.A and Casey, M.A (2008). *Focus groups: a practical guide for applied research*. London: Sage Publications Ltd). This first group will address a number of questions including adolescents' attitudes towards and knowledge of PrEP, in particular, adolescent perceptions of taking drugs previously reserved for HIV treatment as a form of prevention; what some of the barriers and facilitators of PrEP use may be, where they would like to access these drugs outside of the research setting ; whether taking PrEP might identify individuals as high-risk and therefore stigmatise them; whether enhanced protection against HIV infection provided by PrEP might lead to sexual disinhibition or risk compensation; whether adolescents will still use condoms in order to protect against other STI's; and what factors might impact on adherence. This will be seen as perceptions (and identify misperceptions) in a group of as yet uninitiated and perhaps uninformed youth. This data will be gathered and used for the “social marketing objective of CHAMPS-SA, to inform some of the issues that must be considered when creating demand for

youth PrEP. The data will NOT be used to inform the protocol nor will any changes to protocol be made based on this. Parental/ guardian consent and adolescent assent will be obtained for all focus group participants. These FG participants (aged 15-19 years) will be actively recruited from the potential pool of participants for the cohort study.

The second focus group will be conducted in two groups with enrolled participants (n= 6-8 in each separate group) at each site, to be scheduled in the last four weeks of study follow up. It will address a number of questions including participants' attitudes towards PrEP, in particular, their experience taking and general acceptability of the drug; where they would like to access these drugs in the future; whether taking PrEP resulted in identification of individuals as high-risk and stigmatization; whether enhanced protection against HIV infection provided by PrEP led to sexual disinhibition or risk compensation; whether participants still used condoms in order to protect against other STI's; and what factors (such as appearance changes as a result of drug side-effects) impacted on adherence. In addition, they will be asked what the impact of real time (whilst this does not mean on the day of testing, it is used to denote during the study at the next visit) drug levels were in terms of adherence counseling and how they felt about receiving these results at study visits. This data will inform the nature of design of PrEP roll out for youth in the future. Parental/ guardian consent and adolescent assent will be obtained for all focus group participants. In order to ensure a good spread of FG participants, the follow up cohort will be divided into 2 groups: those who chose PrEP and were adherent at least 80% of the follow up time and those who did not choose PrEP or were adherent <50% of the time. 6-8 participants will be randomly selected from each group and then invited to participate in the 2 FGs. The data from these focus groups may be reviewed by Research Ethics Committee members, Data Safety Monitoring Committee members and the sponsors (NIAID), FDA and/or MCC.

4.2 SUMMARY OF MAJOR ENDPOINTS

Primary endpoints:

Acceptability

- The proportion of participants who report willingness to use the study regimen, take up PrEP and remain on PrEP as part of a comprehensive prevention package.

- Assessment of acceptability as per questionnaire administered at study end.

Use

- Number of adolescents who continue to use PrEP (as indicated by DBS/ plasma levels) after the initial 3 month period
- The total time on PrEP for each adolescent (as indicated by DBS/plasma levels) and for the cohort as a whole in those individuals who indicated PrEP use by self report at the beginning of each 3 month period.

Safety

- Grades 2, 3, and 4 clinical and laboratory adverse events;

Secondary endpoints:

Adherence:

- Adherence to daily regimens of oral PrEP as evidenced by the use self-report, pill counts, and proportion of participants on FTC/TDF who have detectable drug levels. Proportion of blood samples with detectable drug levels
- Proportion of adolescents with detectable drug levels who report using PrEP
- Proportion of doses that are taken as instructed.

Sexual and other Behaviors

- Reported number of steady and casual sex partners, condom use (and change after introduction of study product), substance use prior to or during sex, as evidenced by participant responses to interviewer-administered questionnaires and focus groups.
- Proportion of scheduled HIV testing appointments missed, in relation to individual characteristics (age, sex, number of partners, use of other prevention methods) and the characteristics of the product.

HIV infection,

- as measured by seroconversion of study participants during the approximate 12 months of follow-up.

Exploratory endpoints:

Impact on adherence of providing information on drug (FTC/TDF) levels (as measured in Dried Blood Spot/Plasma) given as feedback during counseling sessions.

- Number of counselling opportunities in which drug level feedback is requested vs total number of counseling events
- Number and nature of participants who request drug level feedback.
- Correlation between self reported adherence and drug levels at each visit for each participant
- Correlation between self reported adherence and drug levels at each visit in the study overall.
- Proportion and number of participants whose adherence to study product improves when receiving the results of DBS/Plasma compared to those who do not receive feedback of results as measured by endpoints above.
- Relationship between daily PrEP usage and sexual practices and behavior in adolescents
- Sexual Behaviour Data obtained using a questionnaire and focus groups.
-

4.4 TIME TO COMPLETE ENROLLMENT

The maximum allowable time between screening and enrolment per participant is 40 days.

Following enrollment into the study, each participant will be followed for a total of 12 months.

Time to complete total enrollment of participants is expected to be completed within 8 months.

4.5 EXPECTED DURATION OF PARTICIPATION

All participants will complete 12 months (52 weeks) of study duration in total.

4.6 STUDY SITES

There are two proposed study sites. The first is a site managed by Desmond Tutu HIV Foundation (DTHF) at the Institute of Infectious Disease and Molecular Medicine, University of Cape Town. The DTHF site in Masiphumelele is approximately 20km south of Cape Town where DTHF has been working since 1999. Several cross-sectional and cohort studies focusing on adolescents have been successfully conducted in this under resourced community of 22 000 people. In 2005, DTHF demonstrated that the mean HIV prevalence in the 11-19 yr old was 11%; and the HIV prevalence was 5% in the local high school (the adult HIV prevalence is 26%). Sexual risk assessment suggests that young people in this community practice a range of high risk HIV behaviors. The site has a long-established relationship with community stakeholders, highly experienced study staff, a youth center offering peer-focused activities as well as sexual and reproductive health services, and an active adolescent CAB.

The Perinatal HIV Research Unit (PHRU) site is based in Soweto, near Johannesburg. Soweto is a sprawling collection of formal and less formal townships around 40 kilometres from Johannesburg in Gauteng. It has a population of approx 1 000 000, and an unemployment rate of over 60%. The HIV prevalence of Soweto is approximately 11%, with adolescent prevalence of 2%.

Both sites have worked together with the South Africa AIDS Vaccine Initiative (SAAVI) and the HIV AIDS Vaccine Ethics Group (HAVEG) to develop resources that ensure that the current ethico-legal framework for adolescent involvement in vaccine studies is implemented, and both sites also have well-established adolescent community advisory boards.

5 STUDY POPULATION

5.1 SELECTION OF STUDY POPULATION

The inclusion and exclusion criteria in Sections 5.2 and 5.3 will be used by study staff to ensure the appropriate selection of study participants.

5.2 INCLUSION CRITERIA

Participants must meet all of the following criteria to be eligible for inclusion in the study:

1. Age 15 to 19 years (inclusive) at screening, verified per study site SOPs
2. Able and willing to provide written informed consent/ assent (age dependant) to be screened for and to take part in the study
3. Have a guardian who is able and willing to provide written informed consent for their child to be screened for and to take part in the study
4. Able and willing to provide adequate locator information, as defined in site SOPs
5. HIV-uninfected based on testing performed by study staff at screening and enrollment
6. Sexually active, as defined as a minimum of one act of (penile vaginal)sexual intercourse in the last 12 months, per self-report
7. (For female participants) Negative pregnancy test at screening and enrollment and per participant report, does not intend to become pregnant in the next 12 months
8. (For female participants) Using an effective method of contraception at enrolment, and intending to use an effective method for the study duration; effective methods include low dose oral, implant or injectable hormonal methods.
9. Does not report intention to relocate out of the study area during the course of the study
10. Does not have job or other obligations that would require long absences from the area (> 4 weeks at a time)
11. Willing to undergo all study-required procedures
12. At screening and enrollment, agrees not to participate in other research studies involving drugs or medical devices for the next 12 months

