5.3 EXCLUSION CRITERIA

Participants who meet any of the following criteria, at baseline, are excluded from the study:

- As determined by the Site Investigator, any significant uncontrolled, active or chronic disease process such as but not limited to diabetes, hypertension, and other diseases involving the cardiovascular, pulmonary, gastrointestinal, genitourinary, musculoskeletal, and central nervous systems
- Confirmed \geq Grade 2 hypophosphatemia
- Presence of serious psychiatric symptoms (e.g., active hallucinations)
- Visibly distraught at the time of consent (e.g., suicidal, homicidal, exhibiting violent behavior)
- Intoxicated or under the influence of alcohol or other drugs at the time of consent
- Acute or chronic hepatitis B infection (i.e. if hepatitis B surface antigen positive)
- Hep B seronegative and refuses vaccination.
- Renal dysfunction (Creatinine Clearance < 75 ml/min);
(Use Cockroft-Gault equation:

$$\text{Male} \quad \frac{(140-\text{age}) * \text{Weight(Kg)}}{\text{Serum Creatinine (mg per dl)} * 72} = \text{ml/min}$$

$$\text{Female} \quad \frac{(140-\text{age}) * \text{Weight(Kg)}}{\text{Serum Creatinine (mg per dl)} * 72} = \text{ml/min} * 0.85$$

Serum Creatinine conversion Factors

$$\text{Creatinine (mg/dl)} = \text{Creatinine (\mu mol)} / 88.4$$

$$\text{Creatinine (mg/dl)} = \text{Creatinine (mmol)} / 88.4 * 1000$$

- Urine dipstick for protein and glucose, excluding 1+ or greater
- Any history of bone fractures not explained by trauma
- Any Grade ≥ 2 toxicity on screening tests and assessments
- Concurrent participation in an HIV vaccine study or other investigational drug study
- Known allergy/sensitivity to the study drug or its components
- Use of disallowed medications (see section 6.5)

Note: Otherwise eligible participants with an exclusionary test result may be re- tested during the screening process. If a participant is re-tested and a non- exclusionary result is documented within 40 days of providing informed consent for screening, the participant may be enrolled.

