6.3.1 Pharmacy Facilities and Drug Dispensing

A pharmacist will be responsible for dispensing the drug to each study participant. Only participants with negative HIV test results, will be dispensed the study drug. At enrollment, participants who take study medication will receive a prescription that will include the participant ID. Detailed instructions for receipt, handling, storage, dispensing, accountability, retrieval of unused study products from participants will be provided in site-specific SOPs and South Africa's Good Pharmacy Practice Guidelines.

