7.2 ENROLLMENT VISIT

Day 0 for the participant will be the day of the Enrollment Visit:

- Administrative/Behavioural Procedures

- Locator information (update)
- Review of study procedures (ongoing consent)
- HIV pre-and post-test counseling, including risk reduction counselling
- Provision of condoms
- Eligibility assessment (including review of all screening documentation)
- Baseline sexual risk behavior questionnaire (for all enrolled participants)
- Reimbursement
- Schedule next visit (if applicable)

- Clinical Procedures
 - Review of all prior screening documentation
 - Update medical history and/or current medications, if applicable
 - Re-confirmation (by participant self-report) of medical eligibility information
 - Syndromic treatment for STI, if clinically indicated
 - Offer of STI testing and treatment for participant and partner(s) if indicated
 - Confirmation of current contraceptive method and contraceptive counseling
 - Contraceptive counselling and provision of contraception as appropriate
 - Disclosure of available test results, which must be made available to participant prior to administration of study product
 - Hepatitis B vaccination, if indicated
 - Update Medical History
 - Provision of study drug and instructions

- Laboratory Procedures
 - Urine pregnancy testing (for females)
 - HIV rapid testing
 - At all visits
 - As clinically indicated

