7.3 FOLLOW UP VISITS (FOR WEEKS 4, 8, 12)

All enrolled study participants will complete 4 weekly follow-up visits for the first 12 weeks, targeted to occur every 28 days after the participant's study enrollment date (Day 0). Target dates are set based on the enrollment date, and do not change if subsequent actual visits take place before or after the target date. As it will not always be possible to complete monthly follow-up visits on the targeted dates, follow-up visits may be completed within an approximate 2-week window around the target date (-/+7 days from the target date). Thereafter visits will be 12 weekly with similar windows applying.

The following procedures will be completed at each initial Follow-Up Visits; Wks 4, 8, 12:

- Administrative/Behavioural Procedures
 - Locator information (update)
 - At all visits
 - HIV pre-and post-test counseling, including risk reduction counselling
 - At all visits
 - Social harms and/or benefits
 - At all visits
 - Sexual risk behavior questionnaire
 - At all visits
 - Acceptability questionnaire
 - At all visits
 - Provision of condoms
 - At all visits
 - Reimbursement
 - At all visits
 - Schedule next visit
 - At all scheduled visits, except Final Study Visit
- Clinical Procedures
 - Contraceptive counselling and provision as appropriate
 - At all visits
 - Targeted Physical exam

- As clinically indicated
- Update medical and menstrual history and/or current medications if applicable
 - At all visits
- Record/update adverse events (AEs) applicable
 - At all visits
- Hepatitis B vaccination, if indicated
 - At Enrollment (wk 0), month1 (Wk 4) and Month 6 (Wk 24)
- Provision of study drug and instructions
 - At weeks 4, 8 .
- Laboratory Procedures
 - HIV rapid testing
 - At all visits
 - As clinically indicated
 - STI testing
 - Herpes (HSV-2),
 - Chlamydia and Gonorrhea testing (wk 12 only)
 - Urine dip stick testing
 - Every 3 months; At wk 12 only
 - Aspartate aminotransferase/alanine aminotransferase (AST/ALT) testing
 - Every 3 months; at wk 12 only
 - Serum chemistries, including creatinine, glucose, electrolytes, and lipase
 - Every 3 months, at wk 12 only
 - Full blood count testing
 - Every 3 months; at wk 12 only
 - Haematocrit testing
 - Weeks 4 and 8
 - Urine pregnancy testing (for females)
 - At all visits
 - Contraceptive counseling
 - At all visits

- TDF/FTC drug levels via venous blood sampling and preparation of dried blood spots for storage.
 - At all visits, Wks 4, 8 and 12.

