9.3 PREGNANCY

All participants will be provided with male and/or female condoms. As participants will be required to be sexually active in order to enroll in the study, females will be required to use condoms as well as take low dose, combination oral or injectable hormonal contraception, in addition to receiving contraceptive counseling throughout the duration of study participation. Pregnancy testing is performed at all study visits and participants are encouraged to report all signs or symptoms of pregnancy to study staff. The Site Investigator or designee will discontinue drug permanently, counsel any participant who becomes pregnant regarding possible risks to the fetus according to site SOPs. The Site Investigator/designee also will refer the participant to all applicable services; however, sites will not be responsible for paying for pregnancy-related care. Youth-friendly sexual reproductive health services are available free of charge at care facilities in site surrounds. A

participant who is pregnant will continue to be followed until the pregnancy outcome is ascertained but will not receive any study product.

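### Entry criteria omit breastfeeding, so a participant can be enrolled and given FTC/TDF on Day 0 while already meeting the lactation stopping rule in 9.7

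*Protocol*

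**What the plan says.** Protocol 5.1 makes the two eligibility lists the instrument of selection: "The inclusion and exclusion criteria in Sections 5.2 and 5.3 will be used by study staff to ensure the appropriate selection of study participants". The female-specific items are 5.2 items 7 and 8. Item 7 reads in part "For female participants) Negative pregnancy test at screening and enrollment" and adds that she reports no plan to become pregnant in the next 12 months. Item 8 requires an effective contraceptive method and names oral, implant and injectable hormonal methods. Section 5.3 opens "Participants who meet any of the following criteria, at baseline, are excluded from the study" and lists conditions that do not include breastfeeding.

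Drug is supplied on Day 0: the procedures in 7.2 include "Provision of study drug and instructions". The condition that 6.3.1 sets for dispensing is HIV status: only "participants with negative HIV test results, will be dispensed the study drug".

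Section 9.7 then lists pregnancy and lactation together as a criterion for permanently stopping product, and repeats the item in its list of reasons for ending study participation. Section 13.3 states that no data on excretion of FTC/TDF in human milk have been reported. The SAP contains no eligibility criteria and does not alter any of this.

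**The concern.** The protocol treats lactation as serious enough to end product use for good, but does not look for it before the first dose. Two things follow.

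- If lactation is not recognised on Day 0, an infant who is not a trial participant may be exposed to drugs for which the protocol itself reports no breast-milk data.
- If it is recognised, site staff have an entry rule that admits her and a stopping rule that takes her off product. The eligibility section does not say that she should not have been enrolled as a product user.

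The matter is safety and internal consistency, not estimation.

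**Working it through.** There is no plan figure to reproduce; the check is mainly textual.

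**1. Can a breastfeeding candidate meet every entry rule?** None of the 12 items in 5.2 and no bullet in 5.3 refers to breastfeeding or lactation. A negative pregnancy test, no pregnancy intention and an injectable contraceptive are all compatible with breastfeeding. The investigator-judgement bullet in 5.3 concerns disease processes, which lactation is not.

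**2. Is the gap out of line with the rest of the protocol?** Set the specific 9.7 product-stopping conditions that can be checked at baseline beside the entry criteria:

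| Stopping condition (9.7) | Entry counterpart |
|---|---|
| HIV infection | 5.2 item 5 |
| Pregnancy | 5.2 item 7 |
| Prohibited medication | 5.3, last bullet |
| Product toxicity (9.1) | 5.3, any Grade 2 or higher toxicity; creatinine clearance below 75 ml/min is the cut-off both at entry and in 9.1.3 |
| Lactation | none |

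Lactation is the only one without a match.

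**3. Would a scheduled procedure reveal it?** Neither the screening and enrolment procedures (7.1, 7.2) nor the schedule of events names breastfeeding. At enrolment there is "Re-confirmation (by participant self-report) of medical eligibility information", but with no breastfeeding criterion there is nothing on this point to confirm. The medical history (7.1) and the breast item of the full examination (7.7) might bring it to light. Even then, no line in 5.2 or 5.3 makes her ineligible.

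**4. What does the lactation item in 9.7 add?** Pregnancy by itself already stops drug permanently. Section 7.10.2 says so, and 9.3 has: "The Site Investigator or designee will discontinue drug permanently, counsel any participant who becomes pregnant". The lactation item therefore has its practical effect mainly for someone who is lactating at entry.

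**5. How large is the exposure in an unrecognised case?**
- Girls covered by the gap: 2 × 45 = 90 (sites as described in 4.3) to 2 × 50 = 100 (4.1). This is the group the missing rule applies to, not a count of cases.
- Day 0 to the next scheduled visit: visits are "targeted to occur every 28 days", so 28 daily doses. With the ±7-day window the interval is 28 − 7 = 21 to 28 + 7 = 35 days. A bottle holds 30 tablets (6.3). If one bottle is dispensed, doses cannot exceed 30; the number of bottles is not stated.
- Whole lead-in: 12 × 7 = 84 daily doses.
- Recognised on Day 0 with 9.7 applied at once: 0 doses.

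These are bounds on exposure for one unrecognised case. They say nothing about how often it would happen.

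**The case against.** The textual gap is not in dispute. The case against is about consequence.

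- **A recognised case is protected.** Section 9.7 governs product, so a participant known to be lactating should get none. The PSRT (10.5) also takes queries on eligibility and on withholding the first dose. This stands, and it is why exposure is nil once lactation is recognised. But the PSRT acts only if a site asks, and nothing prompts the question.
- **An unrecognised case needs several misses.** Screening has a medical history, a full examination and contraceptive counselling; enrolment updates the history; weeks 4, 8 and 12 update medical and menstrual history (7.3). To reach 84 doses, lactation must be missed at screening, enrolment, week 4 and week 8. That makes 84 a remote bound. None of these steps asks about breastfeeding by name, however.
- **Other safeguards may exist.** Section 6.3.1 refers dispensing detail to site SOPs, and consent pages are not available for review; either might address breastfeeding. That cannot be ruled out, but 5.1 names 5.2 and 5.3 as the selection criteria, and both are complete.
- **The hazard is not shown.** Section 13.3 reports missing data, not harm, and 2.6.1 notes that FTC is approved from 3 months of age. This tempers the concern. The same section gives TDF approval for HIV treatment only from age 2, and the protocol itself chose lactation as a reason to stop.
- **The item may mean lactation after an on-study pregnancy.** That is a natural reading, because pregnant participants are followed to delivery and opting back in exists. As written, though, the item is not limited in that way and covers anyone lactating on Day 0.

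**Conclusion.** The concern holds. Following the protocol as written, a breastfeeding adolescent can be enrolled and given FTC/TDF on Day 0 while already meeting a criterion for permanent product discontinuation. The potential exposure is about 28 daily doses to week 4 if lactation is missed once drug is dispensed, with a remote upper bound of 84, and none if it is recognised and 9.7 is applied. These figures assume daily dosing as prescribed. The frequency is unknown, because the documents give no breastfeeding prevalence and none is assumed. The primary estimates are not affected in any way that can be shown. The textual gap is certain; its clinical importance depends on how many candidates are breastfeeding and how alert the sites are. It should be corrected, because the correction is cheap and the person at risk is an infant outside the trial.

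**What to change.** Add current breastfeeding to the exclusions in 5.3, so that entry matches 9.7. Add a direct question on breastfeeding to the medical history at screening (7.1) and again at enrolment (7.2), before drug is supplied. Section 4.1 makes opting back in depend on the eligibility criteria, so the same line would also apply at restarts. The gain there is smaller, since 4.3 already rules out restarting when there is a contraindication.

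The cost is one line, one question at each of two visits, and a few candidates who become ineligible. No analysis, sample size or endpoint changes.
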